### ***9.3. Subject Status and Classification***

Subjects who provide written informed consent but do not meet all of the study eligibility criteria will not be implanted or randomized. These subjects will be deemed as “enrolled but not randomized” and their reason for ineligibility will be documented.

Enrolled subjects who are not randomized will not count towards the enrollment cap. Subjects who sign consent, meet all eligibility criteria, undergo permanent implant and are randomized cannot be replaced.

[REDACTED]

[REDACTED]

[REDACTED]

### ***9.5. End-of-Study Action Plan***

When each subject completes the 2-Year Visit or withdraws, the subject exits the study and ends study participation. Subjects may continue to use their system per the applicable Directions for Use and will be followed according to standard of care. Boston Scientific Neuromodulation Corporation will not pay for visits, devices and/or procedures that occur after a subject completes the 2-Year Visit, withdraws or is determined to be lost to follow-up with the exception of the explant procedure. Reimbursement for the explant procedure will be covered by Boston Scientific if performed within 2 months from the end of study date.

If the study is terminated early due to sponsor discretion or due to the discovery of an unexpected, significant, or unacceptable risk/safety concern regardless of how far along the subject has reached in their study follow-up, subjects will be followed according to standard of care. Sites will have 30 days to notify all subjects of study closure.

If device implantation is unsuccessful, the subject will be followed for 2 weeks post implantation attempt to assess for procedure related adverse events. If the device is explanted, the subject will be followed for 30 days post explant to assess for related adverse events.

Device related adverse events and/or deficiencies occurring after study participation, withdrawal from the study, or after the specified timeframe following unsuccessful trials, implant failures, and explants, should be reported to BSN Patient Care at: [contact]. Such complications should not be captured as adverse events in the study.

## **10. Study Methods**

### **10.1. *Data Collection***

The data collection schedule is shown in table below.

**Table 10.1-1: Data Collection Schedule**

	Screening	Opioid Medication Lock Visit	Baseline Period	Baseline Visit	Implant Procedures (Trial and Permanent)	Randomization/ Activation Visit	Programming Lock Visit	3-Month Visit	6-Month Visit	9-Month Visit	1-Year Visit	2-Year Visit End of Study	Unscheduled Visit
		Up to 35 days following informed consent	14 days post-Medication Lock	(0 - 7 days post Baseline Period)	Up to 90 days post-Baseline Visit	Day 0	70 - 14 days	90 + 14 days post randomization	180 ± 30 days post randomization	270 ± 30 days post randomization	365 ± 30 days post randomization	730 ± 30 days post randomization	
Informed Consent (ICF)	X												
Inclusion/Exclusion Criteria Evaluation	—————→												
Demography				X									
Medical History				X									
Beck Depression Inventory (BDI-II)				X			X				X	X	
Oswestry Disability Index (ODI v2.1a)				X			X	X	X	X	X	X	
Short Form Health Survey 36 Item (SF-36v2)				X			X	X	X	X	X	X	
EQ-5D-5L				X			X	X	X	X	X	X	
Pain Intensity (NRS)				X			X	X	X	X	X	X	
Pain Intensity (VRS)				X			X	X	X	X	X	X	
Pittsburgh Sleep Quality Index (PSQI)				X			X	X	X	X	X	X	
Procedure Information					X †								X **
End of Trial Assessment					X								
Programming Parameters ***					X	X	X	X	X	X	X	X	X
Clinician Global Impression of Change (CGI-C)							X	X	X	X	X	X	
Patient Global Impression of Change (PGI-C)							X	X	X	X	X	X	
Percent Pain Relief (PPR)							X	X	X	X	X	X	
Preference Questionnaire								X	X	X	X	X	
Treatment Satisfaction Questionnaire (TSQM 9m)								X	X	X	X	X	
Concomitant Medications (opioid pain medications)		X		X	X	X	X	X	X	X	X	X	X
Adverse Events (AE)	X	X	X	X	X	X	X	X	X	X	X	X	X

Healing Period (0-28 days)

←————— Opioid Medications Locked —————→

\*\* For unscheduled visits where procedures are performed  
\*\*\* Only when device programming is performed  
† The device will remain off after permanent implant until the Activation Visit

**10.2. Study Candidate Screening**

Subjects' eligibility for the study will be assessed based on study Inclusion and Exclusion criteria listed in Sections 9.2 and 9.3, respectively. Subjects who have provided informed consent and who have been determined to not meet all eligibility requirements will be withdrawn.

**10.3. Informed Consent**

Written Informed Consent must be obtained for all patients who are potential study candidates. Study candidates will be asked to sign the Informed Consent form before any study-specific tests or procedures are performed.

- The context of the study must be fully explained to the patient and patients must be given an opportunity to ask questions and have those questions answered to their satisfaction.
- Study personnel should explain to each potential participant that even if he or she agrees to participate in the study and signs an informed consent form, further testing might demonstrate that he or she is not eligible for the study.
- Written informed consent must be recorded appropriately by means of the subject's dated signature.
- The consent process must be documented in the subject's medical chart.

Research study candidates in the State of California will also be provided with the California Experimental Patient's Bill of Rights

**10.3.1. Screening Period**

Subjects undergo screening related procedures to determine eligibility for the study. It may take up to the end of Baseline Visit to complete all eligibility requirements.

[REDACTED]

[REDACTED]

[REDACTED]

[REDACTED]

[REDACTED]

**10.4. Opioid Medication Lock Visit (Up to 35 days following informed consent)**

The Opioid Medication Lock Visit will occur within 35 days following informed consent. However, this visit may occur on the same day as that of the Informed consent as well following completion of consent.

At this visit, the subject’s opioid pain medications will be locked, with no increase in type/dose/route/frequency, until the 3-Month post-randomization Visit.

At this visit (or during the screening period), the investigator will convert the subject’s opioid medication prescriptions from PRN to a fixed dose, as needed.

**10.5. Baseline Period (14 days)**

The Baseline Period will last for 14 consecutive days following the Opioid Medication Lock Visit. At the end of the Baseline Period, subjects will return to the clinic for their Baseline Visit.

Subjects are to not make any increases to their opioid pain medications during this period.

**10.6. Baseline Visit (0 – 7 days post Baseline Period)**

At the Baseline Visit, subjects will return to the clinic to complete remaining screening requirements. Any adverse since the last study visit will be collected.

[REDACTED]

[REDACTED]

[REDACTED]

[REDACTED]

[REDACTED]

[REDACTED]

[REDACTED]

[REDACTED]

[REDACTED]

[REDACTED]

Subjects that meet all study criteria will be scheduled for the device implant procedures (trial and permanent implant of the SCS system). If a subject fails to meet all the eligibility criteria, they will be withdrawn from the study.

**End of Visit Information:**

- Subjects should be reminded not to make any increases to their opioid medications.

**10.7. Implant Procedures (Up to 90 days following the Baseline Visit)**

Subjects will have up to 90 days following the Baseline Visit to receive their Spectra WaveWriter System. Subjects will undergo a trial procedure per standard of care. Following a successful trial, i.e. at least 50% pain reduction in their overall pain as compared with Baseline, the subject will proceed to permanent implantation. Subjects with an unsuccessful

implant procedure will be followed for 2 weeks for procedure related adverse events then withdrawn from the study. Acute opioid pain medications may be taken.

#### **10.8. Healing Period (0 - 28 days following Implant Procedures)**

The subject's device will remain inactivated (device OFF) for up to 28 days following the permanent implantation procedure to allow for healing. Acute opioid pain medications may be taken during this period. No additional scheduled assessments will be completed during this period.

#### **10.9. Randomization Visit (Day 0)**

[REDACTED]

[REDACTED]

[REDACTED]

[REDACTED]

[REDACTED]

[REDACTED]

Information regarding programming parameters will be collected. To aid in programming it is recommended that thoracic and/or lumbar imaging is obtained at this visit or up to 7 days prior to the visit to show the position(s) of the study device lead(s). In the event of suspected lead migration, imaging may be performed to document lead positions.

#### **End of Visit Information:**

- Subjects will receive instructions on the use of the device including the Remote Control and charging system.
- Subjects are to contact the site in an event that any additional intervention is warranted, to report a complaint and/or a suspected adverse event, reprogramming, etc.
- Subjects should be reminded not to make any increase in their opioid pain medications.

#### **10.10. Programming Lock Visit (Day 70 - 14 days post randomization Visit)**

At the Programming Lock Visit, subjects will return to the clinic to have their programs locked. Any protocol required adverse events since the last study visit will be collected.

No further changes to the subject's programs (for e.g. electrode configuration) will be allowed except to resolve a device and/or stimulation-related AE.

Information regarding programming parameters and device information may be collected.

#### **End of Visit Information:**

- Subjects will receive instructions on the use of the device including the Remote Control and charging system, as needed.
- Subjects are to contact the site in an event that any additional intervention is warranted, to report a complaint and/or a suspected adverse event, reprogramming, etc.
- Subjects should be reminded not to make any increase in their opioid medications.

**10.11. 3-Month Visit (90 + 14 days post randomization Visit)**

During the 3-Month Visit, subjects will return to the clinic for study evaluations and programming. Any protocol required adverse events since their last study visit will be collected.

[REDACTED]

[REDACTED]

[REDACTED]

[REDACTED]

[REDACTED]

[REDACTED]

[REDACTED]

[REDACTED]

[REDACTED]

[REDACTED]

[REDACTED]

[REDACTED]

Following completion of assessments, subjects' device will be programmed as needed and programming information may be collected. At this visit, all subjects may receive WaveWriter programming with all available modalities.

- In the event of suspected lead migration or to aid programming the subject's device, imaging may be performed to document lead position.
- Any additional instructions related to charging of the device and/or use of Remote Control may be provided.

**End of Visit Information:**

- Subjects will receive instructions on the use of the device including the Remote Control and charging system, as needed.
- Subjects are to contact the site in an event that any additional intervention is warranted, to report a complaint and/or a suspected adverse event, reprogramming, etc.
- Subjects' opioid medications are no longer locked and can be changed, if needed for the remainder of the study

**10.12. 6-Month Visit (180 ± 30 days post randomization Visit)**

During the 6-Month Visit, subjects will return to the clinic for study evaluations and programming. Any protocol required adverse events since their last study visit will be collected.

[REDACTED]

Following completion of assessments, subjects' device will be programmed as needed and programming information may be collected.

- In the event of suspected lead migration or to aid programming the subject's device, imaging may be performed to document lead position.
- Any additional instructions related to charging of the device and/or use of Remote Control may be provided.

**End of Visit Information:**

- Subjects will receive instructions on the use of the device including the Remote Control and charging system, as needed.
- Subjects are to contact the site in an event that any additional intervention is warranted, to report a complaint and/or a suspected adverse event, reprogramming, etc.
- Changes to opioid pain medications are allowed up to End of Study Visit.

**10.13. 9-Month Visit (270 ± 30 days post randomization Visit)**

During the 9-Month Visit, subjects will return to the clinic for study evaluations and programming. Any protocol required adverse events since their last study visit will be collected.

[REDACTED]

[REDACTED]

[REDACTED]

[REDACTED]

[REDACTED]

[REDACTED]

[REDACTED]

[REDACTED]

[REDACTED]

[REDACTED]

[REDACTED]

Following completion of assessments, subjects' device will be programmed as needed and programming information may be collected.

- In the event of suspected lead migration or to aid programming the subject's device, imaging may be performed to document lead position.
- Any additional instructions related to charging of the device and/or use of Remote Control may be provided.

**End of Visit Information:**

- Subjects will receive instructions on the use of the device including the Remote Control and charging system, as needed.
- Subjects are to contact the site in an event that any additional intervention is warranted, to report a complaint and/or a suspected adverse event, reprogramming, etc.

**10.14. Year 1 and Year 2 Visit (365 ± 30 days post randomization Visit and 730 ± 30 days post-randomization Visit)**

During the 1 and 2 Year Visits, subjects will return to the clinic for study evaluations and programming. Any protocol required adverse events since their last study visit will be collected.

[REDACTED]

[REDACTED]

[REDACTED]

[REDACTED]

[REDACTED]

[REDACTED]

[REDACTED]

[REDACTED]

[REDACTED]

[REDACTED]

[REDACTED]

[REDACTED]

[REDACTED]

Following completion of assessments, subjects' device will be programmed as needed and programming information may be collected.

- In the event of suspected lead migration or to aid programming the subject's device, imaging may be performed to document lead position.
- Any additional instructions related to charging of the device and/or use of Remote Control may be provided.

**End of Visit Information:**

- Subjects will receive instructions on the use of the device including the Remote Control and charging system, as needed.
- Subjects are to contact the site in an event that any additional intervention is warranted, to report a complaint and/or a suspected adverse event, reprogramming, etc.

The 2 Year Visit is the End of Study Visit and End of Study Action Plan (ESAP) will be followed as described in Section 10.5.

**10.15. *Unscheduled Visit***

Subjects may have as many unscheduled visits as required for device-related in-office or procedure visits (e.g., optimization of programming during the programming period) or for evaluation of possible adverse events and if applicable, re-positioning, replacement or explant of a device component. Unscheduled visit information will be captured, as applicable.

**10.15.1. Revision or Replacement of Leads, Extensions and/or IPGs**

During the study, it is possible that leads may be placed incorrectly, migrate, or malfunction and require repositioning or replacement. It is also possible that the extensions or splitters or IPG may be uncomfortable or malfunction and may require repositioning or replacement. The decision to reposition or replace any device component will be made by the investigator and only if the subject agrees. Subjects not agreeing to a recommended lead revision will be withdrawn from the study but will be included in the intent-to-treat and safety analyses. Subjects agreeing to revision will continue study and will be followed according to the original study schedule. Effectiveness data from these subjects will be included in the intent to treat analysis. Lead revisions/replacements for correcting for migration and/or malfunction must be performed as soon as is reasonably possible following determination of the need for revision/replacement.

The investigator should notify Boston Scientific prior to any study procedures. Any replacements or revisions performed during the study should be recorded in the EDC system, including information about the procedure, device, and/or adverse event if applicable.

Information on assessing revisions or replacements of leads, extensions or IPGs as adverse events is described in Safety Reporting Section.

[REDACTED]

[REDACTED]

[REDACTED]

[REDACTED]

**10.17. Study Completion**

All randomized subjects permanently implanted will be followed through completion of the 2-Year Visit or study withdrawal. The End of Study Action Plan defines the actions to be taken when the subject reaches the end of their study participation.

**10.18. Source Documents**

It is preferable that original source documents are maintained, when available. In lieu of original source documents, certified copies are required to be maintained. A certified copy is a copy (irrespective of the type of media used) of the original record that has been verified (i.e., by a dated signature or by generation through a validated process) to have the same

information, including data that describe the context, content, and structure, as the original. Source documentation includes but is not limited to those items noted in Table 10.18-1.

**Table 10.18-1: Source Documentation Requirements**

Requirement	Disposition
Hospital records and/or clinical and office charts including the evidence of but not limited to inclusion/exclusion criteria, informed consent, procedures, exams, SCS System procedure(s) and devices used, evaluations, health economic assessments, laboratory results, medications, assessment of adverse events.	Retained at investigational site
Assessments and questionnaires	Retained at investigational site and/or electronic data collection platform/EDC
Programming information	Retained at investigational site and/or electronic data collection platform/EDC
Imaging films/prints documenting lead(s) location	Retained at investigational site

## 11. Statistical Considerations

### 11.1. Endpoints

#### 11.1.1. Primary Endpoint

The primary endpoint for this study is the proportion of subjects with 50% or greater reduction from Baseline Visit in average overall pain intensity at 3 months post randomization with no increase in baseline average opioid medications used to treat pain.

The percentage of overall pain will be assessed on a scale of 0-100% based on the *Percent Pain Relief (PPR)* questionnaire. Opioids will be calculated for each subject based on *Concomitant Medications*.

#### 11.1.1.1. Hypotheses

The primary statistical hypothesis in this study is that the proportion of subjects with 50% or greater reduction from Baseline Visit in average daily overall pain intensity at 3 months post randomization in the WaveWriter group is non-inferior compared to the Control (i.e. Conventional) group

$$H_0: \pi_t - \pi_c \leq -0.20$$

$$H_1: \pi_t - \pi_c > -0.20$$

Where  $\pi_t$  and  $\pi_c$  are the proportion of subjects with 50% or greater reduction from Baseline in average daily overall pain intensity at 3 months post randomization with no increase in baseline average daily opioid pain medications using Spectra WaveWriter all modalities and conventional settings, respectively. The study's non-inferiority margin is 0.20.

[REDACTED]

11.1.1.3. Statistical Methods

The 95% confidence interval of  $\pi_t - \pi_c$  will be computed. The study will be considered a success if, using the Intent-To-Treat (ITT) analysis, the lower bound of the two-sided 95% confidence interval for the difference is great than -0.20.

[REDACTED]

[REDACTED]

[REDACTED]

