**7. Study Design**

The study is a prospective, multi-center, parallel group randomized controlled trial with an adaptive design. All participants will receive the Spectra WaveWriter Spinal Cord Stimulator (SCS) system and followed per the study schedule as shown in study schematic Figure 8.1-1.

[REDACTED]

Figure 7.1-1: COMBO Study Design

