### 7.2. Treatment Assignment

All enrolled subjects who pass eligibility criteria will receive a trial. Subjects with a positive trial will proceed to receive permanent implant. Following permanent implant, all subjects' device will be randomized in a 1:1 ratio to either receive:

- WaveWriter Settings – Perception and/or sub-perception programming with all available modalities
- Conventional Settings – Perception programming (up to 1.2 kHz)

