**11.2. General Statistical Methods**

**11.2.1. Analysis Sets**

- **Intent-to-Treat (ITT) Population:** All subjects who are randomized regardless of the treatment received.
- **Per Protocol (PP) Population:** All subjects who receive the study device, with no major protocol deviations.
- **Safety Population:** All subjects who sign the IRB-approved written Informed Consent form

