**12.1.2. Direct Data Upload**

For quality assurance purposes and validation, technical data on the SCS device will be collected using direct data upload to the EDC system. BSC Field personnel, who assist in programming the device settings per routine care, will upload the device files into the EDC system.

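### Does non-inferiority judged on ITT, beside a per-protocol set that does not name the assigned programming, leave a gap that needs a change?

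*Combined protocol and SAP*

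**What the plan says.** This text governs subjects enrolled under protocol Versions A-C. The synopsis sends new subjects to Appendix A, which is not in the reviewed text.

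- **Success rule (11.1.1.3).** "The study will be considered a success if, using the Intent-To-Treat (ITT) analysis, the lower bound of the two-sided 95% confidence interval" for the difference in responder proportions must exceed -0.20. Redacted blocks follow directly.
- **Analysis sets (11.2.1).** ITT is everyone randomised, whatever they received. PP is "All subjects who receive the study device, with no major protocol deviations". The visible text does not define which deviations are major.
- **What separates the arms (7, 7.2, 7.3).** "All participants will receive the Spectra WaveWriter Spinal Cord Stimulator (SCS) system". After permanent implant each subject's "device will be randomized in a 1:1 ratio to either receive" WaveWriter settings (perception and/or sub-perception, all modalities) or conventional settings (perception, up to 1.2 kHz). Section 7.3 describes the control arm's programming as limited.
- **Before the endpoint (10.10).** Programs are locked at Day 70 minus 14. The only exception is to resolve a device- or stimulation-related adverse event. At this visit, "Information regarding programming parameters and device information may be collected".
- **At the endpoint (10.11).** Assessments come first, then programming: "At this visit, all subjects may receive WaveWriter programming with all available modalities".
- **Records (Table 10.1-1, 12.1.2).** Programming parameters are marked at the implant procedures, at randomisation, at every later visit and at unscheduled visits, with the footnote "Only when device programming is performed". In addition, "For quality assurance purposes and validation, technical data on the SCS device will be collected using direct data upload to the EDC system".

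**The concern.** In a non-inferiority trial, ITT is not automatically the cautious analysis. If control subjects receive the test treatment, the arms become more alike, and a truly worse treatment can pass. A PP analysis is the usual check, but only if the set removes subjects who did not get their assigned treatment.

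Here the first PP condition, receipt of the device, is met by everyone randomised, so the major-deviation clause does all the work. Every control implant can deliver the test settings, and unscheduled visits for programming are unlimited (10.15). The record also looks loose at first sight: parameters carry a conditional footnote, collection at the lock visit is optional, the uploads are described as quality assurance, and a device file taken after the 3-Month session might show settings that were not in force when pain was measured.

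At stake would be a false claim of non-inferiority with no reliable way of seeing that it came from crossover.

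**Working it through.** **1. Is there a planned crossover before the endpoint?** No. The opening of WaveWriter programming to all subjects in 10.11 follows the assessments, so it cannot dilute the 3-month comparison. Before that, controls are restricted (7.2, 7.3) and programs are locked (10.10). Any earlier use of WaveWriter-only settings in a control departs from the assigned treatment. Section 13 requires deviations to be documented with date and reason.

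**2. Can the settings in force at the endpoint be established?** Yes, largely. The footnote in Table 10.1-1 is not a hole if, as assumed here, the programs available to a subject change only at programming sessions. Recording each session then gives a running history. Section 10.9 says parameters will be collected at randomisation, and 10.15 says unscheduled-visit information will be captured as applicable. Optional wording at the lock visit fits a visit at which no reprogramming may be needed. The settings at the 3-Month assessment are those from the last earlier session, so a file taken after that visit's reprogramming is not essential.

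**3. How large could dilution be?** Sample size, expected rates and crossover are not visible, so this is an illustration. The plan has no visible figure to reproduce, except that a two-sided 95% limit corresponds to one-sided alpha 0.05/2 = 0.025.

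Assumptions: control rate pc = 0.5, 0.7 or 0.8, and n per arm giving about 80% power at true equality. With the normal approximation,

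n = (1.96 + 0.84)² × 2pc(1 - pc) / 0.20².

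This gives 99, 83 and 63; the exact enumeration below used 98, 82 and 63.

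Let the true difference be -0.20, and let a fraction c of controls respond at the WaveWriter rate. Then the WaveWriter rate is pc - 0.20, the control rate is pc - 0.20c, and d = -0.20(1 - c). Approximately,

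P(false success) = Φ[(d + 0.20)/SE - 1.96].

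Worked case, pc = 0.7, n = 83, c = 0.05: the rates are 0.50 and 0.69, so d = -0.19. SE = √[(0.2500 + 0.2139)/83] = 0.0748. Then 0.01/0.0748 - 1.96 = -1.83, and Φ = 0.034.

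Exact binomial enumeration with a Wald interval:

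| Crossover c | pc 0.5, n 98 | pc 0.7, n 82 | pc 0.8, n 63 |
|---|---|---|---|
| 0 | 0.0255 | 0.0256 | 0.0249 |
| 0.02 | 0.0292 | 0.0290 | 0.0280 |
| 0.05 | 0.0356 | 0.0347 | 0.0332 |
| 0.10 | 0.0486 | 0.0459 | 0.0436 |

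If WaveWriter is truly better by 0.10, crossover works the other way: 10% lowers the chance of success from 0.988-0.998 to 0.983-0.997.

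**4. Would a PP set defined by programming be a better check?** Perception programming is allowed in both arms, so a WaveWriter subject can hardly fail such a rule. Exclusions fall almost wholly on controls. Suppose the arms are truly equal and 10% of controls are removed, responding at half the control rate. The remaining control rate is (pc - 0.10 × pc/2)/0.90. For pc = 0.7 this is 0.665/0.90 = 0.739, a spurious difference of -0.039.

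| PP at true equality | Chance of success |
|---|---|
| ITT, for reference | 0.79-0.80 |
| 10% of controls removed, independent of outcome | 0.77-0.79 |
| 10% removed, responding at pc/2 | 0.60-0.65 |
| 10% removed, none responding | 0.40-0.50 |

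**The case for a change.** The strongest case for acting is that the PP definition is itself fully visible and is silent on the one thing that distinguishes the arms. The hypothesis in 11.1.1.1 is also worded in terms of the settings used. If major is settled only at analysis, the judgement could be made with results in view. Crossover would run mainly from control to test, the direction that helps a non-inferiority claim. Naming wrong-arm programming would cost a few words, and PP could stay supportive with ITT decisive.

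Some of this stands. The definition does not list wrong-arm programming, the visible text does not grade deviations, and ITT can be lenient in this design. But the clause already allows the exclusion, and an analyst would be hard put to call control use of test settings before the endpoint anything but major. Whether PP is reported beside ITT, and how major is defined, may be settled in the redacted text, so their absence from view cannot be held against the plan. A doubling of the error needs about 10% crossover, for which the documents give no support. Rewriting PP around programming alone would also drop the existing clause and admit subjects who, for example, broke the opioid lock.

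**Conclusion.** No change is needed. The ITT criterion is not in error. What remains is a missing detail in a supporting analysis set, which analysts can fill sensibly from the programming history and the documented deviations.

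On the assumed rates and sample sizes, false success at a true difference of -0.20 moves from about 2.5% to 2.8-2.9% at 2% crossover and 3.3-3.6% at 5%. It approaches double only at 10% (4.4-4.9%). These are single-stage figures, whereas the design is described as adaptive, so they show scale and are not the trial's error rate. A PP set tied to programming would carry a one-sided selection bias that could exceed the dilution it was meant to detect, so a discordant PP result could not by itself overturn ITT.

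The conclusion rests on three assumptions: the available programs change only at recorded sessions, wrong-arm programming is treated as a major deviation, and crossover before the 3-Month assessments is uncommon, as the restriction and lock intend.
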